Study Rationale	TGR-1202 is a highly specific and orally available phosphoinositide-3-kinase (PI3K) delta (δ) inhibitor with nanomolar inhibitory potency, and high selectivity over the alpha, beta, and gamma Class I isoforms of PI3K. The delta isoform of PI3K is highly expressed in malignant lymphocytes, where it serves as a key node in the B cell receptor (BCR) signaling pathway, thereby making this an attractive target for selective inhibition of malignant B cells. TGR-1202 is currently in a Phase I dose escalation trial, evaluating sequentially higher single agent doses until a maximum tolerated dose (MTD) is determined. Ibrutinib is an inhibitor of Bruton's Tyrosine Kinase (BTK), another key enzyme found at a different point in the BCR pathway, which has been found to be critical for B-cell proliferation and survival (Byrd et al., 2013). Ibrutinib is approved for the treatment of patients with relapsed or refractory Mantle Cell Lymphoma (MCL) and Chronic Lymphocytic Leukemia (CLL). Although ibrutinib monotherapy is a promising therapy for relapsed CLL and MCL, not all patients respond to ibrutinib therapy, and among patients who initially do respond, complete responses have been rare, and resistance mechanisms have already been described, such as the C481S binding site mutations recently reported in CLL. Dual inhibition of both PI3K-delta and BTK holds the promise of both more complete BCR pathway inhibition and also the reduced likelihood of developing treatment resistance. The purpose of this study is to explore the safety and efficacy of the PI3K-delta inhibitor TGR-1202 in combination with the BTK inhibitor ibrutinib, two novel, oral, once daily, targeted agents in patients with select B-cell lymphoid malignancies.
Products	TGR-1202 is a highly specific and orally available PI3K delta (δ) inhibitor available for this study in 200 mg tablets, supplied by TG Therapeutics, Inc. Ibrutinib is an orally available inhibitor of Bruton's Tyrosine Kinase (BTK) commercially available in 140 mg capsules from Pharmacyclics, Inc. / Janssen Pharmaceuticals.
Study Objectives	 Primary Objectives To determine the maximum tolerated dose (MTD) of TGR-1202 when used in combination with ibrutinib in patients with relapsed or refractory CLL or MCL. To evaluate the safety and determine any dose limiting toxicities (DLTs) of TGR-1202 in combination with ibrutinib in patients with relapsed or refractory CLL or MCL. Secondary Objectives To preliminarily characterize the efficacy of TGR-1202 at its MTD in combination with ibrutinib by determining the overall response rate (ORR) defined as the sum of the complete response (CR) and partial response (PR) rate, as well as to determine the rate of nodal response with lymphocytosis (nPR), progression-free survival (PFS), and duration of response (DOR).

	Exploratory Objectives
	To assess whether apoptotic priming as determined by BH3 profiling and pharmacodynamic response as determined by phospho-flow are predictive of clinical response.
Efficacy Endpoints	 Efficacy Endpoints: Overall response rate, defined as sum of CR and PR rates. Responses will be determined according to response criteria as follows: MCL: International Working Group (Cheson et. al 2007; Revised Response Criteria for Malignant Lymphoma, [Appendix A]); CLL: International Workshop for Chronic Lymphocytic Leukemia (IW-CLL) Response Criteria (Hallek et al. 2008 [Appendix B]) as modified by Cheson et al., 2012.
Safety Endpoints	AEs will be evaluated during the treatment period and for 30 days following discontinuation from the study using CTCAE v4.0. The DLT observation period will be the first cycle (28 days).
	Up to 30 subjects per disease group (MCL and CLL/SLL), including a potential 12 qualified patients who will have completed the Phase Ib dose confirmation part of the study, may be enrolled. "Up to" is written because the Phase Ib can potentially stop early. Phase I Dose Confirmation:
	 3 + 3 design using Cycle 1 DLTs for both CLL/SLL and MCL patients, conducted independently in parallel, with a minimum of 3 patients in a cohort, as follows:
	 MCL: 3-6 patients at cohort 1 CLL/SLL: 3-6 patients at cohort 1
Study Design	• If no DLTs are reported among the initial in 3 patients in Cohort 1, the dose level will be considered safely cleared, and dose escalation may proceed to Cohort 2. If no DLTs are reported in 3 patients in Cohort 2, the dose will be considered safe for Cohort 3. If no DLT's are reported among the initial in 3 patients in Cohort 3, the Phase Ib part of the study will open.
	• If 1 DLT is reported in either Cohort 1, 2 or 3, an additional 3 patients will be enrolled. If no additional DLTs are reported ($\leq 1/6$ pts), then dose escalation will continue to the next cohort or Phase Ib (if in Cohort 3 already).
	• If at least two patients experience a DLT in either Cohort 1 (MCL or CLL/SLL), the combination dose will be considered above the maximum tolerated dose and the dose Cohort -1 will enroll 3-6 patients. The same DLT rules will apply for Cohort -1 except if 2/6 patients experience a DLT in Cohort -1 the study will end for that respective group. If at least two

patients experience a DLT in Cohort 2 or 3, the next highest dose level which has cleared DLT evaluation will be considered the dose for the Phase Ib part of the study.

Phase Ib:

Once the dose has been confirmed separately for MCL and CLL/SLL patients, the Phase Ib will open and enroll up to 12 additional patients. The efficacy evaluation will include the 6 patients from the Ph I cohort dose for up to approximately 18 total patients evaluable for efficacy in each patient group (MCL & CLL/SLL).

[figure not shown]
Each Cycle = 28 days Cycle 1:

- TGR-1202 (oral): Starting on Day 1 administered daily in the morning with food, preferably within 30 minutes of a meal
- Ibrutinib (oral): Starting on Day 1 administered daily in the evening

Cycles 2 and >:

Daily treatment with both TGR-1202 and ibrutinib should continue. First efficacy assessment should be approximately 8 weeks (just prior to cycle 3) after Cycle 1/Day 1 (+/- 7 days) and approximately every 12 weeks thereafter (+/- 7 days) through cycle 12 following initiation of therapy (schema below).

Treatment Study Visits

After cycle 12, regular visits should occur every 3 cycles. After the Cycle 15 restaging, disease assessments should occur at least every 6 cycles (+/- 14 days) through cycle 36, at which point assessments can be done per investigator's discretion. After removal from study, patients should be followed for survival approximately every 3 months for up to 2 years

Baseline Lab Evaluation (Local Lab)

- CBC with differential
- Serum chemistry
- Serology to rule out active Hep B, C or HIV infection
- Serum pregnancy test
- FISH cytogenetic analysis
- *IGHV* mutation status (CLL patients only- Test performed by Integrated Oncology- See correlatives section 9.1.2.3)

Instrumenta l Tests

Computed tomography (CT) of the chest, abdomen, pelvis (and neck if palpable cervical adenopathy is present) at screening. Assessments should

CONFIDENTIAL

occur C2D28, C5D28, C9D28, C14D28, then approximately every 6 cycles (+/-14 days) until Cycle 36. Disease assessments after Cycle 36 may be done at the investigator's discretion. After removal from study, patients should be followed for survival every 3 months for up to 2 years or until death, lost to follow up, or initiation of a new CLL/MCL directed therapy

- CT scan and bone marrow biopsy are mandatory for confirmation of a complete response.
- Any patient who achieves a clinical response may have CT scans reviewed and confirmed by independent assessment.

As of June 2014, TGR-1202 continues to enroll patients in a single agent, Phase I dose escalation trial, which has evaluated doses as high as 1800 mg QD. TGR-1202 was subsequently reformulated for greater absorption, and the administration state changed from a fasting state to a fed state, with a dose of 400 mg projected to provide comparable plasma exposure to doses safely cleared in the single-agent study. Ibrutinib is an approved agent for MCL and for CLL/SLL, and is commercially available. TGR-1202 (TGR) and ibrutinib will be administered orally, once per day according to the schedule below. A 3+3 dose escalation design will be utilized to evaluate the dosing cohorts described below. Both the CLL and MCL cohorts will start at dose level 1.

Phase I (Dose Confirmation) - Cycle 1 Schedule

CI (DUSC	Commination, Cy	cic i Schedule			
Dose	TGR Dose	Ibrutinib Dose MCL	Ibrutinib Dose CLL		
Level					
1	400 mg	560 mg	420 mg		
2	600 mg	560 mg	420 mg		
3	800 mg	560 mg	420 mg		
If ≥ 2	DLT's in either Cohort 1,	3-6 pts will enroll in Co	ohort -1 as follows:		
-1	200 mg	560 mg	420 mg		
If ≥ 2 DLT's in a Cohort -1 treatment group, study will be terminated					

Dosing Regimen

Cycle 2 and >

Patients will continue daily administration of TGR-1202 + ibrutinib until progression or removal from study per investigator decision.

The sponsor representative and Principal Investigator will be in charge of

reviewing safety data (SAE's / AE's) after the 3rd patient of each Phase I Cohort (or 6th patient, in the event a DLT occurs among the first 3 patients) completes Cycle 1. They will recommend whether or not it is possible to move into the Phase Ib portion for both the MCL and CLL disease groups independently as per the study design.

Phase Ib:

Once the dose in the Phase I has been confirmed for either the MCL or CLL patient groups, the Phase Ib part of the study will open. All subjects will be treated at the established cohort dose per the same administration schedule from

	the Phase I portion (TGR-1202 and ibrutinib administered on Day 1 of Cycle 1 at the doses noted above and continued daily).
	For all patients at risk for tumor lysis syndrome in the opinion of the treating
	investigator, prophylaxis with allopurinol or per recommended institutional
	standards should be considered.
	Confirmed diagnosis of Mantle Cell Lymphoma (MCL), Chronic
	Lymphocytic Leukemia (CLL), or Small Lymphocytic Lymphoma (SLL)
	• MCL patients must have:
	• At least 1 measurable site of disease according to Revised
	Response Criteria for Malignant Lymphoma
	 Received at least one prior standard therapy for MCL
	 CLL/SLL patients must have:
	 Indication for treatment according to the 2008 IWCLL
	Criteria
	 Received at least one prior standard treatment regimen
	Adequate organ system function, defined as follows:
	• Absolute neutrophil count (ANC) \geq 500 / platelet count \geq 30,000.
	(Patients who have cytopenias due to significant bone marrow
	infiltration do not have to meet hematologic eligibility criteria.
	Significant bone marrow infiltration is defined as >50% involvement by
	CLL.)
	• Total bilirubin \leq 1.5 times the upper limit of normal (ULN), unless due
	to Gilbert's disease or hemolysis, then ≤ 3.0 times ULN.
Inclusion	• Alanine aminotransferase (ALT) and aspartate aminotransferase (AST) ≤
Criteria	2.0 x ULN if no liver involvement or $\leq 4x$ the ULN if known liver
	involvement
	• Creatinine ≤ 2.5 mg/dL OR calculated creatinine clearance ≥ 50 mL/min
	(as calculated by the Cockcroft-Gault method)
	• ECOG performance status ≤ 2
	• Patients must be at least 18 years of age
	In the phase I portion, patients having received prior BTK inhibitors or prior
	PI3K inhibitors are eligible
	Ability to swallow and retain oral medication
	Female patients who are not of child-bearing potential and female
	patients of child-bearing potential who have a negative serum pregnancy
	test at study screening. A tubal ligation is sufficient documentation that a
	patient is not of childbearing potential.
	• Female patients of child-bearing potential, and all male partners must
	consent to use a medically acceptable method of contraception
	throughout the study period and for 30 days after the last dose of either
	study drug. Willingness and ability to comply with trial and follow up procedures
	 Willingness and ability to comply with trial and follow-up procedures, and give written informed consent
Exclusion	• Patients receiving cancer therapy (i.e., chemotherapy, radiation therapy, immunotherapy, biologic therapy, hormonal therapy, surgery and/or
Criteria	immunotherapy, biologic therapy, hormonal therapy, surgery and/or
	tumor embolization) within 3 weeks of Cycle 1/Day 1, with the following

exceptions:

- Patients currently taking ibrutinib do not need to undergo a washout period
- o Limited palliative radiation is allowed if ≥ 2 weeks from C1D1
- Corticosteroid therapy (prednisone or equivalent ≤ 20 mg daily) is allowed as clinically warranted as long as the dose is stabilized at least for 7 days prior to initial dosing. Topical or inhaled corticosteroids are permitted.
- Autologous hematologic stem cell transplant within 3 months of study entry. Allogeneic hematologic stem cell transplant within 12 months. Post-allo patients must not have active graft versus-host disease and be off all immune suppression (other than steroids, as above)
- Evidence of active Hepatitis B (not including patients with prior hepatitis B vaccination; or positive serum Hepatitis B antibody) or active Hepatitis C infection. Evidence of active HIV infection.
- Active central nervous system involvement by lymphoma
- Requires treatment with strong CYP3A4/5 inhibitors (See Appendix J)
- Any severe and/or uncontrolled medical conditions or other conditions that could affect their participation in the study such as:
 - Symptomatic, or history of documented congestive heart failure (NY Heart Association functional classification III-IV [see Appendix H])
 - o QTcF >470 msec
 - o Angina not well-controlled by medication
 - Poorly controlled or clinically significant atherosclerotic vascular disease including cerebrovascular accident (CVA), transient ischemic attack (TIA), angioplasty, cardiac or vascular stenting in the past 6 months
- In the phase Ib portion of the study, CLL patients who have previously received ibrutinib will be ineligible
 - MCL patients who have been on ibrutinib for less than 6 months (180 days) from the time of registration are eligible in the Ib portion of the trial. No washout will be required.

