5.2.2 Cohort Review

The sponsor representative and Principal Investigator will be in charge of reviewing safety data (SAE's / AE's) after the 3rd patient of Cohort 1 (or Cohort 2 and Cohort 3), per MCL and CLL group, is treated on Day 28 of Cycle 1. They will recommend whether or not it is possible to continue to Cohort 2 and 3 or if currently in Cohort 3, move into the Phase Ib portion of the study for each MCL and CLL group independently as per the study design. This decision will be made after a teleconference with the other investigators to obtain their input.

CLL/SLL

Agent	Dose	Route	Schedule	Cycle Length
TGR-	Cohort 1: 400 mg	PO in the a.m. with	Days 1-28,	28 days
1202	Cohort 2: 600 mg	food.*	continuous	(4 weeks)
	Cohort 3: 800 mg			
Ibrutinib	420 mg	PO in the p.m.	Days 1-28,	
			continuous	

^{*} Patients should be instructed to take TGR-1202 with food, preferably within 30 minutes of a meal.

MCL

Agent	Dose	Route	Schedule	Cycle Length
TGR-	Cohort 1: 400 mg	PO in the a.m. with	Days 1-28,	28 days
1202	Cohort 2: 600 mg	food.*	continuous	(4 weeks)
	Cohort 3: 800 mg			
Ibrutinib	560 mg	PO in the p.m.	Days 1-28,	
	_	_	continuous	

^{*} Patients should be instructed to take TGR-1202 with food, preferably within 30 minutes of a meal

The participant will be requested to maintain a medication diary of each dose of medication. The medication diary will be returned to clinic staff at the end of each cycle. See Appendices E and F, MCL and CLL respectively, for diary.

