5.2.3 Phase I Dose Confirmation

The safety of TGR-1202 in combination with ibrutinib will be assessed using a standard 3 + 3 dose-escalation design, with a starting dose of TGR-1202 at 400 mg (Cohort 1) followed by 600 mg (Cohort 2), followed by 800 mg (Cohort 3) and the possibility of a single dose escalation or de-escalation based on safety in the first 3-6 patients in a given cohort. The DLT observation period is the first cycle (28 days). The ibrutinib dose will be fixed at the FDA-approved doses of 420 mg (CLL) or 560 mg (MCL).

A cohort of 3 patients will enter at each dose level. If no DLT is seen in the first 3 eligible patients at any dose level, then a dose escalation will take place.

If 2 or more of the 3 eligible patients experience DLT at dose level 1 (400mg), dose level 2 (600 mg), or dose level 3 (800 mg), the next cohort of 3 patients will be treated at the next lower dose level, unless 6 patients have already been treated at that dose level. If 2 or more of the 3 eligible patients experience DLT at dose level -1 (200 mg), the study will be terminated early.

If 1 of the first 3 patients experiences DLT then 3 additional patients will be treated at that dose level. If there is no DLT in the 3 additional patients then dose escalation will take place. If this is does level 3 or -1, this dose is the MTD. If 1 or more of the 3 additional patients experience(s) DLT then the MTD is considered exceeded, and 3 more patients are treated at the next lower dose, unless 6 patients have already been treated at that dose level. If this is dose level -1, the study will be terminated early.

A minimum of six patients must be evaluated at the highest tolerated dose level prior to proceeding to Phase Ib, and fewer than 2 patients in 6 should experience DLT.

# DLT	Dose Escalation		
0/3	Accrue 3 new patients at next higher dose level. (if this is dose level 3		
	or -1, accrue additional 3 patients at this dose level)		
1/3	Accrue additional 3 patients at current dose level		
1/3 + 0/3	Accrue 3 new patients at next higher dose level (if this is dose level 3		
	or -1, this is the MTD)		
$1/3 + \ge 1/3$	Previous dose level is MTD if 6 treated at that level (if this is dose		
	level -1, terminate the study)		
$\geq 2/3$	1) Prior dose level is MTD (if 6 treated at that level)		
	2) De-escalate dose, accrue additional 3 patients at prior lower level (if		
	only 3 treated at the level thus far) 3) If this is dose level -1, terminate		
	the study		

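### The synopsis opens Phase Ib after 0/3 DLTs in Cohort 3, while 5.2.3 and 13.1 first require six patients with fewer than 2 DLTs; no text says which governs

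*Combined protocol and SAP*

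**What the plan says.** **Synopsis.** Under Study Design, if no DLTs "are reported among the initial in 3 patients in Cohort 3, the Phase Ib part of the study will open". A second group of three is added only when one DLT is seen. Under Dosing Regimen, the safety review is held "after the 3rd patient of each Phase I Cohort (or 6th patient, in the event a DLT occurs among the first 3 patients". The step-down rule after two or more DLTs in Cohort 2 or 3 is that "the next highest dose level which has cleared DLT evaluation will be considered the dose for the Phase Ib part of the study"; it does not say that this lower level must first be filled to six. Under Phase Ib, however, the synopsis also states: "The efficacy evaluation will include the 6 patients from the Ph I cohort dose for up to approximately 18 total patients".

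**Section 5.2.3.** The prose says: "If no DLT is seen in the first 3 eligible patients at any dose level, then a dose escalation will take place". The table qualifies this: after 0/3 at dose level 3 or -1, three more patients are accrued at the same level. The section then states: "A minimum of six patients must be evaluated at the highest tolerated dose level prior to proceeding to Phase Ib". Fewer than 2 of the 6 should have a DLT.

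**Section 13.1.** Escalation after 0/3 is limited to dose levels 1 and 2. After 0/3 at level 3 or -1, three more patients are treated. The minimum of six and the limit of fewer than 2 in 6 are repeated.

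**Sections 5.3 and 13.2.** Phase Ib opens, or its 12 patients are treated, once the MTD has been determined.

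**Sections 5.2.2 and 5.2.4.** Section 5.2.2 places the review "after the 3rd patient of Cohort 1 (or Cohort 2 and Cohort 3), per MCL and CLL group", with a possible move from Cohort 3 into Phase Ib as the study design provides. Section 5.2.4 places it after the last patient of each cohort.

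**The concern.** After 0/3 at 800 mg, the synopsis opens Phase Ib, while 5.2.3 and 13.1 call for three more Phase I patients who can still reject the dose. The MTD is the primary endpoint and sets the dose for 12 further patients per disease, so this branch should have one reading.

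The status of patients 4 to 6 at 800 mg also changes in two practical ways.

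- The DLT definitions in 5.6.3 are headed as applying to Cycle 1 of Phase I only. If these patients count as Phase Ib, the numeric 3+3 rule no longer applies to them.
- Eligibility differs. Phase I accepts patients with prior BTK inhibitor treatment, but "In the phase Ib portion of the study, CLL patients who have previously received ibrutinib will be ineligible". In the CLL group the two readings therefore admit different patients.

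**Working it through.** **Inputs.** The synopsis rule comes from Study Design and the six-patient rule from the 5.2.3 table and 13.1. Table 5 in 13.1 gives escalation probabilities. Let p be the true DLT rate at 800 mg and q = 1 − p.

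**Step 1: the plan's own figure.** Plain 3+3 escalation has probability q³ + 3pq²·q³. For p = 10, 20, 30, 40, 50 and 60% this gives 0.906, 0.709, 0.494, 0.309, 0.172 and 0.082. All six Table 5 values (0.91, 0.71, 0.49, 0.31, 0.17, 0.08) are reproduced. The table describes escalation from levels 1 and 2. At level 3 the same formula is the synopsis rule, not the six-patient rule.

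**Step 2: acceptance of level 3 once reached.**

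- A (synopsis) = q³ + 3pq²·q³
- B (six-patient rule) = q³(q³ + 3pq²) + 3pq²·q³, which equals P(at most 1 DLT in 6)
- A − B = q³ × P(at least 2 DLTs in the next 3)

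B counts 0/3 followed by 1/3 as accepted, because the text asks for fewer than 2 DLTs in 6.

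| p | q³ | 3pq² | A | B | A − B | P(next 3 reject, given 0/3) |
|---|---|---|---|---|---|---|
| 10% | 0.729 | 0.243 | 0.906 | 0.886 | 0.020 | 0.028 |
| 20% | 0.512 | 0.384 | 0.709 | 0.655 | 0.053 | 0.104 |
| 30% | 0.343 | 0.441 | 0.494 | 0.420 | 0.074 | 0.216 |
| 40% | 0.216 | 0.432 | 0.309 | 0.233 | 0.076 | 0.352 |
| 50% | 0.125 | 0.375 | 0.172 | 0.109 | 0.0625 | 0.500 |
| 60% | 0.064 | 0.288 | 0.082 | 0.041 | 0.041 | 0.648 |

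The gap peaks at 7.7 points, at p of about 36%.

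**Step 3: effect over the whole trial.** The documents give no DLT rates for the combination, so this step rests on assumed curves. Write esc(p) for the Step 1 formula. Count only the Cohort 3 0/3 branch, and read step-down as back-filled to six under both texts. The chance that the two rules give a different Phase Ib dose is then

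esc(p at 400 mg) × esc(p at 600 mg) × q³ × P(at least 2 of 3), with the last two terms at 800 mg.

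- Assumed rates 5/10/40% at 400/600/800 mg: 0.973 × 0.906 × 0.216 × 0.352 = 0.067.
- Assumed rates 30/45/60%: 0.494 × 0.234 × 0.064 × 0.648 = 0.005.

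These two are the extremes of nine assumed curves, so the range is 0.5% to 6.7% per disease. In each discordant case the synopsis takes 800 mg forward and 13.1 gives a lower outcome.

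**Step 4: patient numbers.** With no DLTs, the synopsis read literally needs 3+3+3+12 = 21 patients per disease, and the six-patient rule needs 3+3+6+12 = 24. An upward path with every level expanded needs 6+6+6+12 = 30, the stated cap. The back-fill rule already in 13.1 can exceed this. Suppose levels 1 and 2 clear on 0/3, level 3 fails at six, levels 2 and 1 are each back-filled to six and fail, and level -1 is expanded to six and accepted. That is 6+6+6+6 = 24 in Phase I, and 24+12 = 36 in total.

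**The case against.** The strongest reply is that the operative text is largely clear. The 5.2.3 table, its mandatory minimum, 13.1, 5.3 and 13.2 all point to six patients or an established MTD first. The synopsis's own reference to six Phase I patients points the same way, and both the synopsis review text and 5.2.2 defer to the study design. This stands as a guide to what was intended. It does not remove the conflict: the synopsis trigger is explicit, its review timing matches it, and no text ranks one over the other.

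Four stronger readings are tempting, and the documents do not support them.

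- *That 15 patients contradicts 18.* Read literally, the synopsis gives 3+12 = 15 at the dose, but the efficacy total is worded as an approximate upper figure, and 15 falls within it. Only the mention of six Phase I patients conflicts with opening after three.
- *That the third-patient review in 5.2.2 is wrong and should be replaced by the 5.2.4 wording.* A 3+3 design needs that look, because 0/3, 1/3 and 2/3 lead to different actions. The two sections can coexist; what is missing is a further review before Phase Ib.
- *That Phase Ib patients would go unmonitored.* Section 12.2 has the DSMC review toxicity, and the synopsis says Phase Ib can stop early. What is lost is the numeric rule for three patients.
- *That 0/3 is in itself too little evidence.* The one-sided 95% upper limit of 63% after 0/3 applies equally to escalation from levels 1 and 2, which 13.1 accepts.

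The remaining loose wording is ambiguity rather than contradiction: the step-down sentence is silent on back-fill, and the 5.2.3 prose is corrected by its own table.

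**Conclusion.** The contradiction is real and lies in the rule for the primary endpoint; it should be fixed. Followed literally, the synopsis opens Phase Ib at a dose that 13.1 could still reject. Conditional on reaching level 3, the difference in accepting 800 mg is at most 7.7 percentage points. That figure assumes independent DLTs at a common rate and takes the limit of fewer than 2 in 6 as the acceptance rule. Over the whole trial the effect is modest, and its size depends on curves the documents do not supply.

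A reader might infer from 6+6+6+12 = 30 that the stated cap is the most 13.1 can ever require. It is not: the back-fill path in Step 4 reaches 36. Such paths are rare, and they follow from 13.1 as it stands rather than from this correction, but 30 should not be presented as the maximum.

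**What to change.** Align the text with 13.1.

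1. **Synopsis, Study Design.** After 0/3 at dose level 3 (or -1), treat three more patients at that level. Open Phase Ib only with fewer than 2 DLTs in 6.
2. **Synopsis, Dosing Regimen, and 5.2.2.** Keep the review after the third patient of each cohort. Add that the review opening Phase Ib is held after the sixth patient at the selected dose completes Cycle 1.
3. **Synopsis, step-down sentence.** State that the lower level is back-filled to six, with fewer than 2 DLTs, before it becomes the Phase Ib dose.
4. **Section 5.2.3, prose.** Limit escalation after 0/3 to dose levels 1 and 2, as 13.1 does.

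The cost is wording, plus three Phase I patients per disease when no DLTs occur. An ordinary upward path stays within the cap of 30. The sponsor should nevertheless make no statement that 30 is the maximum under 13.1.
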